11.1 Adverse Events

An adverse event (AE) is defined as any untoward medical occurrence in a clinical trial subject administered with a medicinal product and which does not necessarily have a causal relationship with this treatment.

Subjects will be monitored for AEs from the time of Informed Consent Form (ICF) signature until the FU visit (or until EoT, if it occurs more than 30 days after the last CyPep-1 administration for Phase I and Arms A and C and D; for Arm B refer to Clinical Study Protocol Section 7.2.1.3). After the FU visit (or EoT visit, if it occurs more than 30 days after the last CyPep-1 administration), only ongoing AEs or serious adverse events (SAEs) related to CyPep-1 administration will be collected.

A serious AE is any untoward medical occurrence or effect that at any dose:

- Results in death (not due to disease progression),
- Is life-threatening (the subject was at risk of death at the time of the event; it does not refer to an event that hypothetically might have caused death if it were more severe),
- Requires hospitalization or prolongation of existing hospitalization,
- Results in persistent or significant disability or incapacity,
- Is a congenital anomaly or birth defect.

The following are not considered (and do not need to be reported) as SAEs:

- Hospitalization due to a social indication,
- Elective pre-planned hospitalizations for treatment of an existing condition prior to entering the trial,
- Hospitalizations due to tumor-related symptoms or tumor progression.

Any event that does not meet the above criteria may also be considered by the investigator to be an SAE, based on appropriate medical and scientific judgment.

All AEs reported after the start of first dose of study treatment (CyPep-1 or pembrolizumab) are considered treatment-emergent.

AEs will be assessed using CTCAE v5.0, including start and stop dates, severity, relationship to CyPep-1, outcome and action taken. Section 7 of the Clinical Study Protocol provides detailed instructions on AE reporting and definitions related to it.

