- Completion of 18 (for Q6W dosing) administrations (approximately 2 years) with pembrolizumab

(Note: The number of administrations is calculated starting with the first dose of pembrolizumab.)

- Any study intervention-related toxicity specified as a reason for permanent discontinuation as defined in the guidelines for dose modification due to AEs in Section 5.3.6. If CyPep-1 treatment is delayed > 7 days, that dose will be omitted. If the delay of > 7 days is during the TLT observation period, the subject will be replaced.

For Phase I, Phase IIa Arms A and C, if CyPep-1 treatment is delayed for > 6 weeks during the DLT period (first 3 injections), the subject should be discontinued from the trial. For Arm B, treatment with pembrolizumab may continue at the discretion of the investigator. For Arm D, in case CyPep-1 treatment is delayed for > 3 weeks (first 3 injections), the investigator and the Medical Monitor must assess on a case by case basis the decision whether the subject should be discontinued from the trial. Treatment delay due to TEAEs will be considered for treatment discontinuation.

For any subject who is withdrawn or discontinued from the trial, the reason, date and subsequent planned replacement therapy (if applicable), must be recorded in the electronic case report form (eCRF) and in the medical record. (S)AEs ongoing at trial withdrawal will be followed up for outcome information until resolution or stabilization (see Section 7.2.1).

When a subject is withdrawn or discontinued from active trial follow-up after having received at least one intratumoral CyPep-1 injection, and if the subject agreed on the ICF, every effort will be made to report serious adverse events (SAEs) until at least 3 months after the last intra-tumoral CyPep-1 injection administered for both trial phases.

If a subject withdraws consent from specific assessment(s) following intratumoral CyPep-1 injection (i.e. tumor biopsy, radiological or hematological assessments, etc.), all other assessments should be completed as per protocol and a protocol deviation should be recorded for both trial phases.

If a subject is withdrawn or discontinued from the trial, all data collected until the time of withdrawal will be used in the analyses.

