7.1.2 Treatment-Emergent Adverse Event (TEAE)

All AEs reported from the start of the trial (Day 1) are considered TEAEs.

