7.2.1.2 Treatment of Overdose (Arm B)

For this study, an overdose of pembrolizumab will be defined as any dose of 1000 mg or greater.

No specific information is available on the treatment of overdose of pembrolizumab. In the event of overdose, the subject should be observed closely for signs of toxicity. Appropriate supportive treatment should be provided if clinically indicated.

7.2.1.3 Time Period and Frequency for Collecting AE, SAE and Other Reportable Safety Event Information (Arm B)

Specific considerations on safety reporting for Arm B are summarized below:

- All AEs, SAEs and other reportable safety events that occur after the consent form is signed but before treatment /allocation must be reported by the investigator if the participant is receiving placebo run-in or other run-in treatment, if the event cause the participant to be excluded from the study, or is the result of a protocol-specified intervention, including but not limited to washout or discontinuation of usual therapy, diet, or a procedure.
- All AEs or ECIs (Events of Clinical Interest) from the time of treatment/ allocation through 30 days following cessation of study treatment must be reported by the investigator.
- All AEs meeting serious criteria, from the time of treatment/ allocation through 90 days following cessation of study treatment, or 30 days following cessation of study treatment if the participant initiates new anticancer therapy, whichever is earlier must be reported by the investigator.
- All pregnancies and exposure during breastfeeding, from the time of treatment/ allocation through 120 days following cessation of study treatment, or 30 days following cessation of study treatment if the participant initiates new anticancer therapy must be reported by the investigator.
- Additionally, any SAE brought to the attention of an investigator at any time outside of the time period specified above must be reported immediately to the Sponsor if the event is considered to be drug-related.

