7.2.3 Reporting of SAEs

Information on SAEs will be collected from the time of ICF signature until the FU visit (or until EoT, if it occurs more than 30 days after the last CyPep-1 or pembrolizumab administration). After the FU visit (or EoT visit, if it occurs more than 30 days after the last CyPep-1 or pembrolizumab administration), only ongoing AEs or SAEs related to CyPep-1 and / or pembrolizumab administration will be collected.

Specific timing for Arm B is provided in [Section 7.2.1.3](#).

All AEs that meet the criteria for SAE require the completion of a trial specific SAE Form (or Additional Safety Information [ASI] Form), including an assessment of the relationship to the trial drug. This applies to all SAEs, whether or not they were considered to be related to the trial treatment.

The investigator must report all SAEs to [REDACTED] immediately, i.e. within 24 hours (by fax or e-mail) of learning of its occurrence. For this reporting, a SAE Form (provided in the investigator File) needs to be completed in English. The original SAE report form, together with the fax confirmation sheet (if applicable) or e-mail, must be kept at the study site. Follow-up information about a previously reported SAE must also be reported to [REDACTED] within 24 hours of receiving the information. This follow-up data must be provided on an ASI Form or an updated SAE form. The SAE report should provide a detailed description of the AE and should include anonymized copies of hospital records and other relevant documents. Autopsy results, if applicable, should also be sent to [REDACTED] as soon as they become available. Copies of each report will be kept in the investigator File.

All SAEs will need to be followed actively until resolution or stabilization. The above is also applicable to follow-up SAE information.

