11.1.3 Analysis

All AEs will be presented by cohort/arm and overall.

An overview table of treatment-emergent AEs (TEAEs) will be produced, including counts and percentages of subjects (n) and events (#AE) for:

1. TEAEs,
2. TEAEs related to any study treatment (CyPep-1 or pembrolizumab),
3. TEAEs related to CyPep-1,
4. Serious TEAEs (TESAEs),
5. TESAEs related to any study treatment (CyPep-1 or pembrolizumab),
6. TESAEs related to CyPep-1,
7. CTCAE grade 3 or higher TEAEs,
8. CTCAE grade 3 or higher TEAEs related to any study treatment (CyPep-1 or pembrolizumab),
9. CTCAE grade 3 or higher TEAEs related to CyPep-1,
10. TEAEs leading to any study treatment (CyPep-1 or pembrolizumab) discontinuation,
11. TEAEs leading to CyPep-1 discontinuation,
12. TEAEs leading to pembrolizumab discontinuation,
13. TEAEs related to any study treatment (CyPep-1 or pembrolizumab) leading to any study treatment discontinuation,
14. TEAEs related to CyPep-1 leading to CyPep-1 discontinuation,
15. TEAEs related to any study treatment (CyPep-1 or pembrolizumab) leading to pembrolizumab discontinuation,
16. TEAEs leading to CyPep-1 dose reduction,
17. TEAEs leading to pembrolizumab dose reduction,
18. TEAEs leading to CyPep-1 dose interruption,
19. TEAEs leading to pembrolizumab dose interruption,
20. TEAEs leading to study discontinuation,
21. TEAEs leading to study discontinuation related to any study treatment (CyPep-1 or pembrolizumab),
22. TEAEs leading to study discontinuation related to CyPep-1,
23. Dose limiting toxicities (for Phase I and Phase IIa Arms A and C),
24. Treatment limiting toxicities (only for Arm B),
25. Fatal TEAEs,
26. Fatal TEAEs related to any study treatment (CyPep-1 or pembrolizumab),
27. Fatal TEAEs related to CyPep-1.

Adverse events will be coded based on the MedDRA (version specified in the *Data Management Plan*) for reporting by SOC and PT. SOC will be ordered in accordance with the international agreed upon sort order for SOC followed by descending order of overall PT incidence within the SOC.

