13 APPENDIX

13.1 APPENDIX 1. PARTIAL DATE CONVENTIONS

ALGORITHM FOR TREATMENT EMERGENCE OF ADVERSE EVENTS:

For AEs with missing or partial start and end dates, the following imputation rules will be applied (i.e., “worst case” scenario):

AE start datetime:

Impute to *treatment start datetime* if:

- *AE start time* unknown and *AE start date* = *treatment start date*.
- *AE start day* is missing from *AE start date* and *AE start month* = *treatment start month*.
- *AE start month* is missing from *AE start date* and *AE start year* = *treatment start year*.
- *AE start datetime* fully missing.

Else impute *AE start datetime* as earliest possible datetime (i.e., 00:00 if time unknown, first day of month at 00.00 if time and day unknown or 1st of January at 00.00 if time, day and month are unknown).

AE end date:

If *AE end day* and/or *AE end month* is missing, *AE end day* and /or *AE end month* is imputed with the last day of the month and/or last month of the year. If the imputed *AE end date* falls after *end of study date*, the *AE end date* is imputed with the *end of study date*.

Fully missing AE end dates won't be imputed, unless end date is missing and AE is marked as not resolved at time of death – in that case, AE end date will be imputed as date of death.

Imputed AE start and end dates will only be used for analysis purposes (e.g., generating summary tables or figures). In the listings, the incomplete study dates will be presented as collected (i.e., as incomplete).

An algorithm for determining treatment emergence of an AE is given in [Table 6](#) below.

Table 6. Algorithm for Treatment Emergence of Adverse Events

Start date	Rule
Known	If AE start datetime < treatment start datetime , not TEAE. If AE start datetime ≥ treatment start datetime , then TEAE.
Partial/Missing	If imputed AE datetime < treatment start datetime , not TEAE. If imputed AE datetime ≥ treatment start datetime , then TEAE.

ALGORITHM FOR MEDICATIONS AND PROCEDURES PRIOR / CONCOMITANT / SUBSEQUENT TO STUDY TREATMENT:

Partial start datetime

Impute to *treatment start datetime* if:

- *Start time* unknown and *start date*=*treatment start date*.
- *Day* is missing from *start date* and *start month*=*treatment start month*.
- *Month* is missing from *start date* and *start year*=*treatment start year*.

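### Treatment-emergent AEs have no end date while the written SAE collection periods differ by arm, so Arm B serious-event percentages may be biased upward against monotherapy

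*SAP*

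**What the plan says.** **Definition.** SAP 11.1 states: "All AEs reported after the start of first dose of study treatment (CyPep-1 or pembrolizumab) are considered treatment-emergent". The algorithm in SAP Appendix 1, Table 6, agrees: "If AE start datetime ≥ treatment start datetime , then TEAE". Protocol 7.1.2 is equally open-ended: "All AEs reported from the start of the trial (Day 1) are considered TEAEs". None of the three gives a last day.

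**Collection of SAEs.** Four places in the protocol set the period:

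- Section 7.2.1.3 (Arm B): "through 90 days following cessation of study treatment, or 30 days following cessation of study treatment if the participant initiates new anticancer therapy". The shorter of the two periods applies. The Adverse Events text in section 6.2 repeats this.
- Section 7.2.3 (general rule): "Information on SAEs will be collected from the time of ICF signature until the FU visit", or until EoT if that falls more than 30 days after the last dose. After that, only ongoing events related to trial treatment are collected. Footnote 3 of the schedule makes 30 days the minimum time to the FU visit.
- Section 4.3.1: for subjects withdrawn or discontinued from active follow-up after at least one injection, in both phases and if they agreed on the consent form, "every effort will be made to report serious adverse events (SAEs) until at least 3 months after the last" CyPep-1 injection.
- Footnote 21 of the schedule, which also serves the Arm B tables, ends AE reporting at the FU visit (or late EoT) and does not mention 90 days.

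Non-serious AEs in Arm B stop at 30 days after cessation (7.2.1.3).

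**Presentation.** SAP 11.1.3: "All AEs will be presented by cohort/arm and overall". The overview table gives counts and percentages for serious, Grade 3 or higher and fatal treatment-emergent events. SAP 8.10 adds totals pooled over arms. No exposure adjustment is stated. Laboratory, vital-sign, ECG and ECOG summaries are restricted to the on-treatment period of SAP 8.5, but AE summaries are not.

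**The concern.** With no end to the definition, the period at risk for a treatment-emergent SAE is whatever period was collected. On the written rules that can be 90 days after treatment in Arm B and about 30 days elsewhere. A crude percentage rises with time at risk, so at equal true hazard the Arm B column can be higher only because SAEs were looked for longer. The pooled totals mix the two periods.

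The rows affected are serious and fatal treatment-emergent events, and the Grade 3 or higher row through its serious subset. Within Arm B, serious events may be counted for 60 days longer than non-serious ones, so the serious share of AEs can also rise.

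Type and number of AEs, as monotherapy and in combination, is a primary endpoint. A reader who compares Arm B with Cohort 3 and Arm A could not separate combination toxicity from longer ascertainment. SAP 11.1 refers Arm B readers to protocol 7.2.1.3, so the different period is acknowledged, but no analysis rule deals with it.

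**Working it through.** The plan gives no SAE rate and no figure for this point, so there is nothing to reproduce. The calculation below is an illustration.

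**Inputs from the documents**
- Post-treatment window: 90 or 30 days in Arm B (7.2.1.3); 30 days in the other arms, the minimum time to the FU visit (7.2.3, footnote 3).
- Arm B size: 15.
- Days per month: 30.4375 (SAP 8.4).

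**Assumptions (not in the documents)**
- Constant SAE hazard *h*, identical in both groups, from 0.03 to 0.20 per month.
- Time on treatment *T* from 2 to 6 months.
- A share *s* of Arm B starts new anticancer therapy by day 30 and so has the 30-day window.
- No deaths in the extra days.

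**Formulas**
- Monotherapy: P = 1 − exp(−h × (T + 30/30.4375)).
- Arm B with the full window: P = 1 − exp(−h × (T + 90/30.4375)).
- Difference: (1 − s) × exp(−h × (T + 0.986)) × (1 − exp(−h × 1.971)), where 1.971 = 60/30.4375 months.

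The middle factor of the difference is the chance of no SAE before the extra days begin. Only those subjects can gain a first SAE.

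**Results for T = 4 months, s = 0**

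| h per month | Monotherapy | Arm B | Difference | Subjects of 15 |
|---|---|---|---|---|
| 0.05 | 22.1% | 29.4% | +7.3 points | 1.1 |
| 0.10 | 39.3% | 50.1% | +10.9 points | 1.6 |
| 0.15 | 52.7% | 64.8% | +12.1 points | 1.8 |

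Check of the middle line: exp(−0.10 × 4.986) = 0.607 and 1 − exp(−0.10 × 1.971) = 0.179. Their product is 0.109.

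**Range over h = 0.03 to 0.20 and T = 2 to 6 months**
- s = 0: +4.7 to +17.9 points.
- s = 50%: +2.3 to +9.0 points.
- s = 80%: +0.9 to +3.6 points.
- s = 100%: 0.
- Section 4.3.1 applied to every monotherapy subject: about 0, since 3 months is about 90 days.

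**Scale.** The exact 95% interval for 5 of 15 subjects is 11.8% to 61.6%.

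**With one window for all arms,** the difference due to the window is 0 by construction at every hazard.

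**The case against.** The strongest reply is that unequal periods are not established. Section 4.3.1 covers subjects who are withdrawn or discontinued, in both phases, and subjects with confirmed progression are taken off-trial (section 6.2, footnote 23). The 3-month effort can be read to reach much of the monotherapy population, and where it applies the windows are about equal. The FU visit is a minimum of 30 days rather than a cut-off, and Arm B drops to 30 days once new therapy starts. All of this stands. It does not equalise the arms, because 4.3.1 depends on consent and on best effort, and monotherapy subjects who stop treatment but stay in follow-up fall under the FU-visit rule.

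Three stronger readings are tempting, and the documents do not support them:

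- *That combination SAE rates are inflated as a matter of fact.* No rate is given, and the difference can be about zero.
- *That the extra 60 days add a first SAE in 9%, 18% or 26% of Arm B at 0.05, 0.10 or 0.15 per month.* Those values, 1 − exp(−h × 60/30.4375), apply only to subjects with no earlier SAE. After allowing for earlier SAEs over an assumed 4 months on treatment they become 7.3, 10.9 and 12.1 points.
- *That all Grade 3 or higher events gain time.* Non-serious ones in Arm B stop at 30 days.

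The trial's own exclusions also limit the effect. Deaths due to progression and hospitalizations for tumor-related symptoms or progression are not SAEs (protocol 7.1.5, SAP 11.1), so part of the post-progression background is not counted. TLTs are confined to Cycle 1 and are unaffected. No between-arm test of AEs is planned, Arm B differs in population (progression on anti-PD-1/L1 therapy is required), related serious events have their own rows, and study day of onset is listed.

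Finally, a 30-day limit alone could hide relevant events, since protocol 5.3.6.2 warns that immune-related AEs may appear several months after the last pembrolizumab dose. This stands, and the fix must keep the full-period total.

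**Conclusion.** The open-ended definition and the disagreement between protocol 4.3.1, 7.2.1.3, 7.2.3 and footnote 21 are plain in the text. Followed as written, the plan can place unequal SAE periods side by side and pool them on a primary endpoint. The supportable conclusion is that Arm B serious-event percentages **may** be biased upward against monotherapy.

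The direction is firm if Arm B has the longer period and hazards are equal, because extra days cannot lower a cumulative percentage. The size is uncertain: about 0 to 18 points over the assumed range, and about 1 to 2 of 15 subjects at 0.05 to 0.15 per month with 4 months on treatment and no new therapy. It shrinks towards zero if most subjects start new therapy early or if 4.3.1 is applied fully.

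This is a cheap improvement and not a must-fix. The tables are descriptive, the arms are not randomized, and with 15 subjects the sampling uncertainty is larger than the effect.

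**What to change.** 1. In SAP 11.1 and Table 6, add an upper limit common to all arms for the side-by-side and pooled rows, for example onset up to 30 days after the last dose of any study treatment. Anchoring on any study treatment matters in Arm B, where one drug may continue after the other stops.
2. Show SAEs with later onset in a separate row, beside the full-period SAE total, so that late immune-related events remain visible.
3. Declare the departure from protocol 7.1.2 in SAP 4.3, which now reports no discrepancies with the protocol.
4. Reconcile the SAE collection periods in protocol 4.3.1, 7.2.1.3, 7.2.3 and footnote 21, and state which period applied to each arm.

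The first three steps cost SAP wording and a few extra table rows, and the fourth a protocol clarification. The downside is that late events are split from the main row, including any monotherapy events first recorded at an FU visit held after day 30. The full-period total keeps them in view.

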7.2.2 Documentation of AEs

All AEs are to be evaluated for duration, intensity, and relationship to (associated with) the trial treatment or due to other causes including underlying disease.

All AEs (problems, complaints, signs, and symptoms and clinically relevant laboratory abnormalities), both those observed by trial site personnel and those spontaneously reported by the trial subjects, must be recorded on the AE page in the eCRF, as well as in the subject's medical record using standard medical terminology **regardless of causality**. If an AE occurred after signing the ICF, but the subject withdraws from the trial before receiving any trial treatment, the AE should be recorded in the eCRF.

Each event should be recorded as a single diagnosis. Accompanying signs (including abnormal laboratory values, physical examination findings, pulmonary or cardiovascular function tests) or symptoms should not be recorded as additional AEs. However, if the diagnosis is unknown or uncertain, signs and symptoms must be recorded. As soon as the diagnosis causing the signs and symptoms is known, the event terms will be adjusted to the final diagnosis.

For each AE, a minimum required information should be reported, which includes:

- The type of AE,
- An estimate of its severity (using NCI-CTCAE version 5.0, see [Appendix C](#)),
- Date and time of occurrence,
- Date of resolution,
- Actions required,
- An assessment of its causal relationship to trial medication (using the WHO system for standardized case causality assessment, provided separately in the investigator File).

AEs resulting from disease relapse/ progression themselves are not considered to be an AE. Likewise, any medical condition that is present at the Screening Visit will be considered as baseline and will not be reported as an AE but as medical history. However, if the condition changes at any time during the trial, it will be recorded as an AE. Investigators should ensure that the event term recorded captures the change in the condition (e.g., “worsening of...”).

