7.2.2.1 Severity of AEs

Each AE is to be classified and graded according to CTCAE v5.0 criteria (see [Appendix C](#)). Dates of onset and resolution, including dates at which the grade of an AE changes, are to be recorded in the subject file.

If no CTCAE grading is available, the severity of an AE is to be graded as follows:

- **Mild (Grade 1):** the event causes discomfort without disruption of normal daily activities.
- **Moderate (Grade 2):** the event causes discomfort that affects normal daily activities.
- **Severe (Grade 3):** the event makes the subject unable to perform normal daily activities or significantly affects his/her clinical status.
- **Life-threatening (Grade 4):** the subject was at risk of death at the time of the event or the event caused death.
- **Death (Grade 5):** death related to an AE.

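### SAP Table 6 classifies treatment emergence by onset alone, so a fully dated AE that starts between the Screening Visit and first dose and worsens after dosing is left out of the TEAE summaries

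*SAP*

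**What the plan says.** AE collection starts before treatment. SAP 11.1 says: "Subjects will be monitored for AEs from the time of Informed Consent Form (ICF) signature until the FU visit". Screening opens on Day -28 in the protocol's schedules of assessments, so an AE can start before first dose.

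Three statements define treatment emergence:

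- Protocol 7.1.2: "All AEs reported from the start of the trial (Day 1) are considered TEAEs".
- SAP 11.1: "All AEs reported after the start of first dose of study treatment (CyPep-1 or pembrolizumab) are considered treatment-emergent".
- SAP Appendix 1, Table 6, for a known start date: "If AE start datetime < treatment start datetime , not TEAE". A start at or after treatment start is a TEAE. A partial or missing start date is imputed first and then put through the same comparison.

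None of the three mentions an increase in grade.

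Two recording rules in the protocol also matter. Section 7.2.2 says "any medical condition that is present at the Screening Visit will be considered as baseline and will not be reported as an AE". Such a condition is medical history, and a later change in it becomes an AE whose term must describe the change. Section 7.2.2.1 says that dates of onset and resolution, "including dates at which the grade of an AE changes, are to be recorded in the subject file". It does not ask for a new AE record when the grade changes.

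**The concern.** The type and number of AEs is a primary endpoint (Protocol 2.2.1, SAP 5.2.1), and almost every AE summary in SAP 11.1.3 is restricted to TEAEs. A definition based only on onset ignores deterioration on treatment of an event that was already under way. If that deterioration happens after the injection, the summaries lose an event that the safety evaluation is meant to capture.

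The wording is also inconsistent. Protocol 7.1.2 and SAP 11.1 turn on when an AE is reported, while Table 6 turns on when it starts. An event that starts on Day -7 and is first reported after dosing is a TEAE under the SAP 11.1 text and is not one under Table 6.

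**Working it through.** The plan gives no figure to reproduce, so the check is to trace Table 6 through the possible cases. Treatment start is the first dose of either study drug (SAP 8.3).

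| Case | How it is recorded | Result under Table 6 |
|---|---|---|
| (a) Condition present at the Screening Visit, worse after dosing | Medical history, then a new AE for the worsening (Protocol 7.2.2) | TEAE at the worsened grade, if the new record is dated at the change |
| (b) AE starting after the Screening Visit and before first dose, full start date, worse after dosing, kept as one record | Original start date stands; the grade-change date is in the subject file (Protocol 7.2.2.1) | Not a TEAE |
| (c) As (b), but the day is missing and the month is that of treatment start, or the month is missing and the year matches, or the date is fully missing | Start imputed to treatment start (SAP Appendix 1) | TEAE |
| (d) Laboratory worsening | CTCAE shift from baseline to maximum grade (SAP 11.4) | Shown whatever the TEAE status |

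Only case (b) is lost. Its course through the outputs in SAP 11.1.3 is as follows.

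1. It leaves the summaries of all TEAEs, related TEAEs, serious TEAEs, Grade 3 or higher TEAEs, and TEAEs leading to discontinuation.
2. It enters the pre-treatment AE table, item 23 of the summaries by SOC and PT. Tables with a grade breakdown are named as such in that list (items 2, 6, 12, 14 and 17), and item 23 is not. The post-dose grade is therefore not shown there.
3. It stays in the listing of all AEs. If it meets the DLT or TLT definition, it also appears in items 20 or 21 and the matching listings, which are not labelled as restricted to TEAEs.

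Steps 1 and 3 together allow the outputs to disagree. A related event that reaches Grade 3 in Cycle 1 can be in the DLT table and absent from the Grade 3 or higher TEAE table.

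Effect per subject on the incidence of the affected term, if the subject has no other TEAE under that term, is 1/n at the planned arm sizes:

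- Arm A, n = 9: 1/9 = 11.1 percentage points
- Arm B, n = 15: 1/15 = 6.7 percentage points
- Expanded Arm A, n = 18: 1/18 = 5.6 percentage points

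The number of such subjects cannot be derived from the documents. If 2% to 10% of subjects were affected (an assumption with no source in the plan), the expected count would run from 9 × 0.02 = 0.2 in Arm A to 18 × 0.10 = 1.8 in expanded Arm A, which is about 0 to 2 subjects per arm.

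**The case against.** The strongest reply is that little is left once the plan's other rules are applied. Much of that reply stands.

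- A reader might infer that no screening-onset event that worsens can ever be a TEAE. Cases (a) and (c) show otherwise, and case (d) covers laboratory values.
- A reader might infer that the worst grade is reported as pre-treatment. The pre-treatment table lists no grades, so the event count goes there and the grade does not.
- A reader might link the gap to the injection-site pain reported at 5 mg/mL (Protocol 5.3.4). Pain recorded as an injection-site event cannot start before an injection, so it is a TEAE. A screening biopsy could cause earlier pain, but the sample may be up to 90 days old and is not taken if the lesion is inaccessible, the procedure is unsafe or the subject declines.
- A reader might infer that the SAP's AE conventions as a whole favour the drug. Its other defaults go the opposite way: missing severity becomes Grade 3, missing relationship becomes related and missing seriousness becomes serious (SAP 11.1.3).
- In Arm B, Protocol 7.2.1.3 requires pre-treatment AEs to be reported only in limited situations, so fewer records are exposed there.
- The single-record premise is not stated in the plan. Protocol 7.2.2.1 says where grade-change dates go, not whether the eCRF splits the record, and the eCRF guidance is not among the documents.

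Two further replies only partly succeed. The schedules show Screening as one column from Day -28 to Day 1. If the Screening Visit meant that whole window, the medical-history rule would absorb case (b). But AEs are collected from consent, and both Protocol 8.1.3 and the SAP plan a separate summary of pre-treatment events, which would then have almost nothing to report. The DLT and TLT tables are a real backstop, but only for related events that meet those definitions, in the main in Cycle 1. A rise from Grade 1 to Grade 2, or most worsening after Cycle 1, is not caught.

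**Conclusion.** The concern holds for case (b) only. There Table 6 states a rule that gives the wrong classification on a primary safety endpoint, and no other text in the two documents corrects it. The affected event is absent from every TEAE-based summary, but it can still be found in the listing of all AEs and, where it qualifies, in the DLT/TLT tables.

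The size is 11.1, 6.7 or 5.6 percentage points per affected subject for the affected term at n = 9, 15 or 18. The frequency is unknown and may be zero. Within case (b) the error can only lower treatment-emergent counts and grades. The documents do not support a claim that the trial's AE rates are materially understated overall.

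This rests on three assumptions: the eCRF keeps one record through a grade change, the Screening Visit is not the whole screening window, and the worsening record in case (a) is dated at the change. The protocol implies the last of these but does not state it.

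**What to change.** In SAP 11.1 and Table 6, define a TEAE as an AE with onset on or after first dose, or with onset before first dose and an increase in CTCAE grade (or becoming serious) on or after first dose. Count the second kind at its post-dose grade. Align the reporting-based wording in SAP 11.1 and Protocol 7.1.2 with Table 6, so that one rule applies. State whether the eCRF captures such worsening as a new record or as a dated grade change.

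Before database lock, query AEs that start before first dose and end after it or are ongoing. Use the grade-change dates in the subject file to classify them, and document the decisions at the Data Review Meeting (SAP 7.1).

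The cost is one clause in the SAP, a matching edit to the protocol definition and a small data query. TEAE counts may rise slightly.
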